1. In patients who fail traditional non-ultrasound IV catheter placement, compare ultrasound-guided cannulation of AccuCath catheters versus ultrasound-guided cannulation of conventional IV catheters in ED patients across the following clinical parameters: first attempt success rate, procedure time from the point of first percutaneous puncture to successful cannulation, total number of percutaneous punctures required for successful cannulation, and total number of IV

- catheters required for successful cannulation.
- 2. Assess patient and provider satisfaction with each catheter system on a 5-point Likert scale.
- 3. Check for clinical and demographic differences between patient groups that were successfully cannulated on first attempt versus those that required multiple attempts.

We hypothesize that:

- 1. Ultrasound-guided cannulation of AccuCath IV catheters will demonstrate a higher first attempt success rate, require less procedure time, require fewer percutaneous punctures, and utilize fewer catheters than ultrasound-guided cannulation of conventional IV catheters in ED patients.
- 2. Patients and providers will be more satisfied with AccuCath IV catheters versus conventional IV catheters in the ED setting.
- 3. There will be no statistically significant clinical and demographic differences between patient groups that are successfully cannulated on first attempt versus those that required multiple attempts.

Methods

I. Subject population (Patients)

- a. Inclusion criteria
 - English speaking patients, male or female, aged ≥18 years presenting to the UCMC Mitchell ED with Emergency Severity Index (ESI) from 1 to 5 anytime during Monday through Sunday.
 - Capable and willing to provide informed consent
 - Acceptable candidate for ultrasound-guided PIV per Mitchell ED protocol (i.e. 3 failed attempts by nurses- 2 by primary nurse, 1 by senior nurse)

b. Exclusion criteria

- Lack of decisional capacity (e.g., intoxication, dementia, delirium, developmental delay)
- Prior venous grafts or surgery at target IV site

II. Subject population (Providers)

UCMC emergency faculty and resident physicians.

III. Study implementation

1. Provider consent

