We will obtain oral consent from UCMC emergency faculty and resident physicians, and nurses who have previously undergone ultrasound-guided PIV training, scheduled to work in the Mitchell Emergency Department during the study period. Typically, providers will be consented for participation in the study as group during academic conference hours or during ultrasound-guided PIV training sessions for nurses.

2. Patient recruitment and IV placement

We will use an unbiased mechanism for identifying a random cohort of ED patients. We will generate a randomization schedule for two treatment groups using 25 blocks of 20 patients. We expect to enroll a total of 500 patients in our study, 250 patients in each treatment arm.

A written patient consent form will explain that patients will be randomized to receive either ultrasound-guided cannulation of an AccuCath catheter (Group A) or ultrasound-guided cannulation of a

conventional IV catheter (Group B). The consent form will also explain that anonymized records of their clinical and demographic information will be used for research purposes. Patients will be able to refuse to participate in our study.

If a patient agrees to participate in the study, he or she will undergo either ultrasound-guided cannulation of an AccuCath catheter or ultrasound-guided cannulation of a conventional PIV catheter, both of which are currently used in clinical practice. Following ultrasound-guided IV cannulation, patients will be asked to respond to survey questions that will assess patient satisfaction with the IV catheter received and will document past history of IV drug use, smoking, dialysis, difficult IV stick, diabetes, sickle cell disease, cancer chemotherapy, hypertension, and congestive heart failure.

3. Provider's assessment

Providers will be required to complete a standardized form documenting the ultrasound-guided IV cannulation procedure. The form will ask for: laterality of IV site, number of percutaneous punctures, procedure time, number of IV's used, overall satisfaction with IV catheter.

4. Data acquisition

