All patients admitted to the ED at UC are identified using hospital and physician records, including patient age, gender, and race. Relevant demographic data along with emergency severity index, body mass index, blood pressure, and past history of IV drug use, smoking, dialysis, difficult IV stick, diabetes, sickle cell disease, cancer chemotherapy, hypertension, and congestive heart failure will be collected from the patients or extracted from EPIC and used to understand the demographic and clinical characteristics of our study participants, with PHI exclusions. The analysis of the data will help us understand the generalizability of our findings based on the characteristics of our study population.

Protocol Duration

2 years

Research Location(s)

UCMC (Mitchell Hospital, Emergency Department)

Special Precautions

Special precautions will be taken throughout the data collection process, including:

1. Performance results of AccuCath vs conventional IV catheters

In order to avoid influencing care decisions, all clinicians and patients will be blinded to aggregate performance results comparing AccuCath IV versus conventional IV catheters. Only study personnel will have access to aggregate results comparing AccuCath IV with conventional IV catheters.

2. MRN and Study ID

The study ID will be linked to the MRN in a password-protected database. No one besides the specified study personnel will have access to the records or data.

3. Clinical Data

Clinical data will be entered directly to a password-protected database. No one besides the specified study personnel will have access to the records or data.

4. Satisfaction survey data

Patient satisfaction survey data will be entered directly to a password-protected database. No one besides the specified study personnel will have access to the records or data.

5. Provider's assessment data

Providers will indicate their assessment of catheter performance on a form that will be collected and accessed only by the study personnel. The data will be transferred to a password-protected database, and the physical copies will be destroyed as soon as data transfer is completed.

Statistical Analysis

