Our primary outcome will compare the first attempt success rate of ultrasound-guided AccuCath IV cannulation versus that of ultrasound-guided conventional IV cannulation in ED patients. Our sample size of 250 patients for each treatment group has been 80% powered to detect a difference of 10% (2-sided, α =0.05). Our secondary outcome measures include procedure time from the point of first percutaneous puncture to successful cannulation, total number of percutaneous punctures, total number of IV catheters used, and patient satisfaction.

We will also check for clinical and demographic differences that may have contributed to difficult venous access.

Potential Benefits and Risks to Subjects

The risks associated with the use of our experimental catheter are comparable to the anticipated risks of standard IV therapy, which include infection, infiltration, extravasation, phlebitis, dislodgement, bleeding, hematoma, and pain at IV site. There is possibility that the experimental catheter's guidewire could cause intimal damage, but the guidewire has been designed specifically to minimize this risk, which is shared by conventional IV catheters.

References

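### Blinding covers only aggregate results, and the plan does not say whether patients are told their device before they rate it, so patient satisfaction is open to expectation bias

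*Combined protocol and SAP*

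**What the plan says.** All references are to the combined protocol and SAP.

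- **Blinding.** Special Precautions, item 1, is the only place where blinding appears: "all clinicians and patients will be blinded to aggregate performance results comparing AccuCath IV versus conventional IV catheters". Its stated purpose is "In order to avoid influencing care decisions". Protection of satisfaction ratings is not mentioned.
- **Consent.** Methods III.2 says the written consent form explains randomization to one of two groups. It identifies Group A by the product name AccuCath and Group B as a conventional IV catheter. It does not say whether the individual assignment is then disclosed or withheld.
- **Rating.** The same section says that after cannulation "patients will be asked to respond to survey questions that will assess patient satisfaction with the IV catheter received". It does not say who gives the survey.
- **Scale and hypothesis.** Objective 2 is to "Assess patient and provider satisfaction with each catheter system on a 5-point Likert scale". Hypothesis 2 is directional: "Patients and providers will be more satisfied with AccuCath IV catheters versus conventional IV catheters in the ED setting".
- **Status.** Statistical Analysis ends its list of secondary outcomes with "total number of IV catheters used, and patient satisfaction". It gives no test, SD or target difference for satisfaction.
- **Provider rating.** Methods III.3 has the provider record satisfaction on the procedure form.

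**The concern.** Satisfaction is the patient's opinion. Of the listed outcomes it is the one most exposed to what the patient expects of the device. The provision that looks like blinding hides the running comparison between arms, not the patient's own catheter. With no instruction either way, each operator decides whether to name the device, and the survey then asks the patient to judge that device.

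The patient half of hypothesis 2 is at stake. If patients know their device, a higher AccuCath score could reflect shorter or less painful placement, or it could reflect the label or the operator's manner. The plan records nothing about what patients knew or believed, so the analysis could not tell these apart afterwards.

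**Working it through.** The plan gives no figure for satisfaction, so there is none to reproduce. The check asks how small a pure rating shift would be enough to produce a significant result.

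**Inputs from the documents**
- 250 patients per arm (Methods III.2; Statistical Analysis).
- Two-sided α = 0.05. The plan states this for the primary outcome only; it is borrowed here.
- A 5-point Likert scale (objective 2).

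**Assumptions, not in the documents**
- SD of the score: 0.8, 1.0 or 1.2 points.
- Size of any expectation shift: 0.1, 0.2 or 0.3 points.
- No true difference between devices.

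**Step 1. Smallest significant observed difference**

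SE = SD × √(2/250) = SD × 0.0894. Smallest significant difference = 1.96 × SE.

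- SD 0.8: 1.96 × 0.0716 = 0.14 points
- SD 1.0: 1.96 × 0.0894 = 0.18 points
- SD 1.2: 1.96 × 0.1073 = 0.21 points

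**Step 2. Chance that a pure shift b gives p < 0.05**

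Probability = Φ(b/SE − 1.96) + Φ(−b/SE − 1.96).

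| Shift b (points) | SD 0.8 | SD 1.0 | SD 1.2 |
|---|---|---|---|
| 0.1 | 29% | 20% | 15% |
| 0.2 | 80% | 61% | 46% |
| 0.3 | 99% | 92% | 80% |

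**Step 3. Cross-check with a rank test**

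This used a Mann-Whitney test, 2,000 simulated trials per setting, and an assumed score distribution of 5/10/20/35/30% over scores 1 to 5 (mean 3.75, SD 1.13). A given share of AccuCath patients rate one point higher from expectation alone, capped at 5. Because 30% already score 5, the mean shift is 0.7 × that share.

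| Share shifted | Mean shift (points) | Trials with p < 0.05 |
|---|---|---|
| 0% | 0 | 4.9% |
| 20% | 0.14 | 32% |
| 30% | 0.21 | 63% |
| 40% | 0.28 | 86% |
| 50% | 0.35 | 97% |

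The two approaches agree: a shift of about a fifth of a point gives a significant result in roughly half to four fifths of trials, depending on the SD. This shows what would be sufficient, not what is likely.

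**The case against.** The strongest reply is that the point rests on silence. No section says that patients are told their device, and neither the survey nor the consent form is available to us. A reader might infer that patients will know their arm and that the satisfaction result will therefore be biased. The documents do not support that; they leave the matter open. That part of the reply stands, and the point is limited to the missing instruction.

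A reader might also infer that patients are rating a novelty. Potential Benefits and Risks to Subjects does refer to "The risks associated with the use of our experimental catheter", but that is protocol wording and nothing shows that patients see it. Methods III.2 says that both catheters are already in clinical use. Withholding aggregate results may also dampen expectations somewhat, although it does not hide the device.

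Feasibility is a fair objection. Background & Significance describes an integrated guidewire and a different catheter material. Patients must have decisional capacity and have just had three failed attempts, so some will notice which device is used. Masking would be partial. Provider ratings cannot be masked at all, so that half of hypothesis 2 stays exposed whatever is done for patients.

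Finally, the arithmetic would apply to any unmasked rating in a trial of this size. It is no evidence that a shift of 0.2 points will occur here. That also stands.

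None of this supplies the missing instruction or gives a reason to leave it out.

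**Conclusion.** The concern holds in a limited form. The plan's blinding protects care decisions from interim comparisons. It does not address whether patients know their own device when they rate it, so the patient half of hypothesis 2 is open to expectation bias, and the plan has no means of detecting it.

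At 250 per arm, an observed difference of about 0.14 to 0.21 points would be significant. That rests on an assumed SD of 0.8 to 1.2 and a borrowed two-sided 0.05. Whether any expectation effect exists, and how large it would be, cannot be taken from the documents.

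A reader might extend this to the trial's main result. It does not reach that far: the primary outcome is first attempt success, which does not depend on patient ratings, and its sample size is not in question here. This is an inexpensive improvement to one subjective secondary outcome, not a flaw in the main comparison.

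**What to change.** In Methods III.2, state the following:

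1. After consent, which may still name both devices and their risks, operators do not name the assigned device to the patient until the satisfaction survey is completed.
2. The survey item is worded neutrally, for example as satisfaction with the ultrasound-guided IV placement.
3. One added survey item asks which device the patient thinks was used, so that the success of masking can be reported alongside the result.

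In Statistical Analysis, state that provider satisfaction is reported as unblinded, because the operator handles the device.

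The cost is one instruction to operators, a change of survey wording and one extra question. It needs no additional staff, visits or patients. The downside is that masking is partial, since some patients will see or recognise the device; the added item shows how often they identify it correctly.

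I would not ask for a rewritten consent form, which has to be free to describe device-specific risks such as the guidewire's. Nor would I require the survey to be completed away from the operator, since the plan does not say who gives it and this might need another person.

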Project Title

Randomized, Controlled Study of Ultrasound-Guided Peripheral Venous Access Using AccuCath Versus Ultrasound-Guided Conventional Intravenous Catheter in the Emergency Department

Principal Investigators

[name] [name], MBA, MSc

Co-Investigators

[name], MBA, MS

Background & Significance

Peripheral venous cannulation is among the most common procedures performed in clinical settings and is a prerequisite for fluid resuscitation, administration of medications, and diagnostic testing^{1,2}. In the United States, approximately 300 million peripheral intravenous catheters (PIV) are inserted annually¹, and more than 25% of all visits to the emergency department require intravenous catheters for parenteral fluid administration³. Providers in the emergency department have become adept at establishing peripheral venous access, but it is estimated that PIV insertion fails for 6 million patients annually¹.

Many factors are thought to be associated with difficult venous access, which is typically defined to be at least two failed attempts at establishing intravenous access³. Intravenous drug abuse, obesity, multiple hospitalizations, and chronic medical problems including diabetes, sickle cell disease, end-stage renal disease, and cancer are predisposing factors for difficult venous access²⁻⁵. Prior studies have reported prevalence of difficult venous access ranging from 8% to 23%²⁻⁵. Failure to establish peripheral venous access in the emergency department is a costly problem, leading to delays in diagnostics and treatment and requiring alternative sites for vascular access such as external jugular, intraosseous, or central venous access³. These alternative methods can lead to higher complications rates, decrease patient satisfaction, and increase utilization of nursing and physician time⁶. Central venous catheterization, which is often used when traditional venous cannulation methods fail, has an overall complication rate of 15%, and complications include arterial puncture, pneumothorax, deep vein thrombosis, and infection^{7,8}. These complications pose a significant financial burden to the healthcare system, as the cost associated with a single central venous catheter related infection in 2002 was estimated to be \$34,508 to \$56,000 and the median payout for claims resulting from central venous catheter related injuries was \$100,750².

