Nevertheless, studies to date on ultrasound-guided peripheral venous cannulation have revealed some shortcomings. Conventional IV catheters placed under ultrasound guidance have been prone to premature failure with failure rates of 8% ^{7,17} in the first hours after placement and 47% in the first 24 hours, most commonly due to infiltration ⁷. These failure rates are significantly higher compared with 2% at 24 hours and 10% at day 4, which has been reported for standard peripheral IV catheters ^{7,19}. Moreover, while overall success rates range from 90% to 100% with multiple attempts ^{2,7,13,20}, first attempt success rate has been less impressive, ranging from 46% to 71% ^{13,20}. Our study will assess whether the AccuCath catheter with its integrated guidewire can address these shortcomings and demonstrate superiority over conventional PIV catheters across clinical outcomes relevant to the emergency department setting.

While catheters with guidewires have long been used when placing central and arterial lines, they have largely been absent from PIV placement. The AccuCath catheter is differentiated from conventional IV catheter in two principal ways. The catheter material consists of polyether block amide, which is a thermoplastic elastomer with softness and flexibility designed to decrease vessel wall irritation and mechanical phlebitis²¹. In addition, the integrated guidewire facilitates catheter insertion and limits vessel damage²¹. A prospective, randomized, controlled study has shown a first attempt success rate of 89% for AccuCath versus 47% for conventional IV along with lower complication rates of 8% for AccuCath and 52% for conventional IVs²¹. This study was performed in an inpatient setting on patients receiving elective, non-emergent PIVs²¹. Our study will be important in determining whether AccuCath's superior first attempt success rate and lower complication rate can be replicated in emergent PIVs in the emergency department setting. These improvements could translate to cost savings from decreased utilization of physician and nursing time, fewer number of PIV catheters used, higher patient satisfaction from fewer percutaneous punctures, and less complications from infiltration and phlebitis.

Purpose & Hypotheses

The objectives of the study are to:

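### The primary comparison uses no baseline covariate; prespecified adjustment for BMI and IV drug use would be a cheap improvement with a small, possibly zero, gain

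*Combined protocol and SAP*

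**What the plan says.** - **Primary analysis (Statistical Analysis):** "Our primary outcome will compare the first attempt success rate of ultrasound-guided AccuCath IV cannulation versus that of ultrasound-guided conventional IV cannulation". The section gives 250 patients per arm, 80% power, a 10% difference and two-sided alpha of 0.05. It names no test, model or covariate.
- **Predisposing factors (Background & Significance):** "Intravenous drug abuse, obesity, multiple hospitalizations, and chronic medical problems including diabetes, sickle cell disease, end-stage renal disease, and cancer are predisposing factors" for difficult access.
- **Data collected (Methods III.4):** BMI, IV drug use and other history items, from patients or from EPIC. The stated use is to describe participants and judge generalisability.
- **Timing (Methods III.2):** the history items, including IV drug use, are documented in a survey given after cannulation, together with the satisfaction questions.
- **Other planned use (Purpose & Hypotheses, objective 3):** "Check for clinical and demographic differences between patient groups that were successfully cannulated on first attempt", against those needing several attempts. Statistical Analysis adds a similar check for contributors to difficult access. Neither adjusts the comparison between arms.
- **Randomisation (Methods III.2):** 25 blocks of 20, with no stratification factor named.

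**The concern.** The plan regards certain patient characteristics as related to difficult access and collects them, but uses them neither in the randomisation nor in the primary comparison. If they also predict first-attempt success under ultrasound, adjusting for them narrows the confidence interval for the risk difference without extra patients.

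The choice has to be made in advance. The plan names no model, collects many candidate covariates and schedules a look at them by first-attempt result. A covariate set chosen after results by arm are known would expose the primary result to a charge of selection.

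Timing also matters. IV drug use is a pre-procedure characteristic, but an answer given after cannulation could be coloured by how the procedure went. It is a safe adjustment variable only if its value is fixed beforehand.

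**Working it through.** **Inputs.** From the documents: 250 per arm, two-sided alpha 0.05, and a difference read as 10 percentage points. Background & Significance says of ultrasound-guided placement that "first attempt success rate has been less impressive, ranging from 46% to 71" per cent; this is background, not a stated design rate. Assumed, because no document gives them: IV drug use prevalence of 15% and the covariate odds ratios below.

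**1. The plan's own figure.** With p1 the control rate, p2 = p1 + 0.10 and p̄ their mean,

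n per arm = [1.960·√(2p̄(1−p̄)) + 0.842·√(p1(1−p1) + p2(1−p2))]² / 0.10².

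At 75% vs 85%: (1.960·√0.320 + 0.842·√0.315)² / 0.01 = 250. So 250 per arm gives 80.0% power at about 75% vs 85%. The formula gives 391.1 (so 392) per arm at 46%, 356 at 60% and 285.1 (so 286) at 71%.

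**2. Effect of adjustment by formula.** If the covariates explain a fraction R² of the outcome variance, the effective n per arm is 250/(1−R²): 255.1 at R² = 0.02 and 263.2 at R² = 0.05.

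| Control vs AccuCath | Power, R² = 0 | R² = 0.02 | R² = 0.05 |
|---|---|---|---|
| 46% vs 56% | 60.9% | 61.8% | 63.2% |
| 60% vs 70% | 65.0% | 65.9% | 67.3% |
| 71% vs 81% | 74.6% | 75.5% | 76.8% |
| 75% vs 85% | 80.0% | 80.8% | 82.0% |

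The 95% CI half-width at R² = 0 and 0.05 goes from 8.72 to 8.50 points at 46% vs 56%, and from 7.44 to 7.25 points at 71% vs 81%. The equivalent in patients is 500/(1−R²) − 500, which is 10 at R² = 0.02 and 26 at R² = 0.05.

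**3. Which R² is plausible for two covariates.** For one binary predictor with 15% prevalence and an assumed 20-point gap in success, R² = 0.20²·0.15·0.85/(p(1−p)). This is 0.022 at an average success rate of 65% and 0.028 at 76%.

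A simulation of the proposed model (6,000 trials of 500 patients, blocks of 20) compared the standardised risk difference with robust SE against the unadjusted pooled z-test. Each cell shows power unadjusted, then adjusted:

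| Odds ratios (per SD of BMI / IV drug use) | R² | 46% vs 56% | 60% vs 70% | 71% vs 81% |
|---|---|---|---|---|
| 1 / 1 | 0 | 62.9 → 62.2% | 66.0 → 66.0% | 75.3 → 75.6% |
| 0.80 / 0.67 | 0.011–0.017 | 62.7 → 62.2% | 65.9 → 66.7% | 75.5 → 76.3% |
| 0.67 / 0.50 | 0.036–0.050 | 63.3 → 63.6% | 65.4 → 67.8% | 75.1 → 77.1% |

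Each power carries a Monte Carlo SE of about 0.6 point, so the smallest changes should not be over-read. Adjusted type I error was 4.9% to 5.4% (SE 0.3).

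At 46% vs 56% the simulated power gain falls short of the formula's partly because the unadjusted z-test is slightly liberal there. Its exact type I error is 5.36%, and its exact power is 62.4% against 60.9% by formula. By formula the interval still narrows, but power hardly moves.

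**4. Can adjustment restore 80% power?** The R² required is 1 − 250/n: 1 − 250/391.1 = 0.36 at 46%, 1 − 250/356 = 0.30 at 60%, and 1 − 250/285.1 = 0.12 at 71%. All exceed the 0 to 0.05 above.

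**The case against.** The strongest reply is that nothing is broken. With 1:1 blocked randomisation, a simple comparison of proportions is valid and a legitimate preference. The listed factors are predictors of difficult access in general, not of first-attempt success under ultrasound. Everyone enrolled has already had "3 failed attempts by nurses- 2 by primary nurse, 1 by senior nurse", which may leave little prognostic spread. The investigators themselves expect none: "There will be no statistically significant clinical and demographic differences between patient groups that are successfully cannulated on first attempt". IV drug use, half of the proposed model, is documented after the procedure, and the completeness of EPIC for it is unknown. The more basic gap is that no test is named at all.

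Most of this stands. It limits the size of the point and rules out calling it a defect. It does not remove the case for deciding now: the cost is wording and one collection step, and the loss if the covariates are uninformative is negligible.

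Three stronger readings might be inferred, and the documents support none of them:

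- **That the unadjusted result would be biased or invalid.** Randomisation protects it.
- **That the gain is larger than stated.** Odds ratios of 0.55 per SD of BMI and 0.45 for IV drug use (assumed 20% prevalence, control success about 50%) would cut the variance by about 12%. Nothing in the documents points to effects of that size.
- **That unrecorded operators undermine the comparison.** Methods II names "UCMC emergency faculty and resident physicians", while Methods III.1 adds "and nurses who have previously undergone ultrasound-guided PIV training", and the provider form lists no operator field. These passages need reconciling, but that is a separate point and not part of this claim.

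**Conclusion.** The point holds as a low-cost improvement. The plan names no covariate for its primary comparison although two candidate factors are among the data it collects. A two-covariate model cuts the variance by 0 to about 5%, worth about 0 to 2 power points or 0 to about 26 patients in total. The power gain is near nil at a 46% control rate.

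These sizes rest on assumed odds ratios between 1/1 and 0.67/0.50 and an assumed 15% prevalence of IV drug use. A gain of zero is possible. A reader might infer that adjustment rescues the stated 80% power. It does not: 250 per arm reaches 80% only at about 75% vs 85%, and across the 46% to 71% background range power stays below 80% with or without adjustment. Equally, that background range is not a stated design rate, so this point does not show that the trial is underpowered.

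**What to change.** Before any outcome data are seen, write into Statistical Analysis:

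1. The primary analysis is a logistic regression of first-attempt success on arm, BMI and history of IV drug use. The list is closed, with no provision to add factors later.
2. The result is reported as a standardised risk difference with a robust 95% CI, which keeps the scale of the 10-point design target.
3. The unadjusted comparison is kept as a sensitivity analysis.
4. IV drug use is taken from EPIC, which Methods III.4 already allows, or asked before randomisation. The answer in the post-cannulation survey is not used for adjustment. If neither route is workable, adjust for BMI alone.
5. Missing covariate values are handled by a rule set in advance that uses neither arm nor outcome.

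**Cost.** SAP wording and either a chart extraction or one question asked earlier; no extra patients. The downsides are a slightly more complex model, possible missing BMI or EPIC history values, and a variance increase of about 1% if both covariates are uninformative (simulated variance ratio 1.01).

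### 250 per arm does not give 80% power for a 10-point difference at any conventional-catheter first-attempt rate the protocol cites (46% to 71%); power there is about 61% to 75%

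*Combined protocol and SAP*

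**What the plan says.** The Statistical Analysis section defines the primary comparison: "Our primary outcome will compare the first attempt success rate of ultrasound-guided AccuCath IV cannulation versus that of ultrasound-guided conventional IV cannulation". The only sample-size justification follows: "Our sample size of 250 patients for each treatment group has been 80% powered to detect a difference of 10" percent ("2-sided, α =0.05"). It states no conventional-arm rate, test or formula.

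Under Study implementation, the enrolment target is the same number: "We expect to enroll a total of 500 patients in our study, 250 patients in each treatment arm". There is no allowance for missing outcomes.

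The Background & Significance section gives the only first-attempt rates for conventional peripheral catheters. For ultrasound-guided placement, "first attempt success rate has been less impressive, ranging from 46% to 71" percent. For the cited randomised inpatient comparison, "first attempt success rate of 89% for AccuCath versus 47% for conventional IV"; the protocol does not say whether that study used ultrasound.

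**The concern.** A 10-point difference between two proportions is easier to detect when both lie near 0 or 1 and hardest near one half. A claim of 80% power for 10 points with 250 per arm therefore cannot be checked without a conventional-arm rate, and the protocol states none. The rates it cites lie in the middle of the scale, where 250 per arm looks too few.

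This is the only numerical support for the size of the trial. If the claim fails at the cited rates, the chance of missing the difference the protocol chose as its target is larger than the stated 20%, and readers of a non-significant result would credit the trial with more sensitivity than it had.

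**Working it through.** **Inputs**
- n = 250 per arm, 1:1 allocation; two-sided α = 0.05; target difference d = 0.10, read as percentage points (Statistical Analysis).
- Conventional-arm rate p₁: not stated. I use 46% to 71% (Background), with 47% from the cited randomised comparison as a further point inside that range.
- No loss of outcomes, since the enrolment target equals the powered number.

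**Formulas** (pooled-variance normal approximation)

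Let p₂ = p₁ + 0.10, p̄ = (p₁ + p₂)/2, A = √[2p̄(1 − p̄)], B = √[p₁(1 − p₁) + p₂(1 − p₂)].

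- Power = Φ[(d√n − 1.960·A)/B]
- n per arm for 80% power = (1.960·A + 0.8416·B)²/d²

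**Step 1: reproduce the plan's figure.** At 75% vs 85%, p̄ = 0.80, A = √0.32 = 0.5657 and B = √0.315 = 0.5612.
- n = (1.960 × 0.5657 + 0.8416 × 0.5612)²/0.01 = 250.
- Power at n = 250 is 80.0%.

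So the printed figure is exactly right for 75% vs 85%. Solving for every conventional rate that gives 80% yields 0.750 and its mirror image 0.150. Between these two values power is below 80%.

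**Step 2: the cited rates.** Here d√n = 0.10 × √250 = 1.5811.
- At 46% vs 56%: A = 0.7070, B = 0.7034, so z = (1.5811 − 1.3857)/0.7034 = 0.278 and power = 60.9%.
- At 71% vs 81%: A = 0.6040, B = 0.5998, so z = (1.5811 − 1.1838)/0.5998 = 0.662 and power = 74.6%.

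| Conventional rate | Power for +10 points, 250 per arm | n per arm for 80% | Difference detectable with 80% power |
|---|---|---|---|
| 46% | 60.9% | 392 | 12.5 points |
| 47% | 61.0% | 391 | 12.5 points |
| 50% | 61.4% | 388 | 12.4 points |
| 60% | 65.0% | 356 | 11.8 points |
| 71% | 74.6% | 286 | 10.6 points |
| 75% (not cited) | 80.0% | 250 | 10.0 points |

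**Step 3: does another method or reading rescue the claim?**

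| Method or reading | Power at 46% | Power at 71% |
|---|---|---|
| Unpooled variance | 61.3% | 75.1% |
| Arcsine | 61.0% | 74.9% |
| Exact enumeration, uncorrected chi-square | 62.4% | 74.9% |
| Exact enumeration, Yates-corrected chi-square | 59.0% | 71.4% |
| 10-point decrease | 62.4% | 65.6% |
| 10% relative increase | 17.6% | 44.5% |
| One-sided test | 72.4% | 83.6% |

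No two-sided version reaches 80% in the range. A one-sided test does so only near the top (78.8% at 65%, 82.7% at 70%), and the plan specifies two-sided.

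**Step 4: other rates in the Background.** The 90% to 100% figures are overall success after multiple attempts. The 77.3% is single-pass internal jugular cannulation. Neither is a first-attempt rate for a conventional peripheral catheter, so neither supplies the missing assumption.

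**The case against.** The best defence is that the printed statement is not false in itself: 75% vs 85% gives exactly 250 per arm, and the true rate at this site is unknown. The 46% to 71% range is offered as literature background, not declared as the planning assumption, and trained emergency operators might do a few points better. At 71% the gap is small: 75% power instead of 80%, or a detectable difference of 10.6 points instead of 10. This is fair, and the 61% to 75% should be read as power at the cited rates. But the protocol never states or argues for 75%. That value lies above every conventional first-attempt rate it cites, and its patients have already failed three nurse attempts.

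A second defence is that the trial rests on a far larger effect. At 47% vs 89%, power with 250 per arm is essentially 100%; at half that effect (47% vs 68%) it is still about 99.8%, and for a 15-point difference it is 92% at 46% and 98% at 71%. This is also correct, and it limits the practical damage: the shortfall bites only for true effects near 10 points. Yet 10 points is the target the protocol chose, and it asks whether results from elective inpatients carry over to emergency placement.

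Two smaller points stand. The 47% cannot be called an ultrasound-guided rate on the text given, but the range does not need it. And the protocol sets no rule for reading a null result; even true 80% power would not let one rule out 10 points.

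**Conclusion.** The concern holds. Taking 10% as percentage points, with a two-sided 0.05 test, 250 per arm and no missing outcomes, power for the stated target is 61% to 75% across the conventional first-attempt rates the protocol cites. The chance of missing a true 10-point benefit is about 25% to 39%, not 20%. Keeping the 10-point target at 80% power would need 286 to 392 per arm, or 572 to 784 in total. The stated figure requires a conventional rate of about 75%, which appears nowhere in the document. Any lost outcomes would lower power further.

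This must be fixed because it is the sole power statement for the primary endpoint and it disagrees with the protocol's own evidence over the whole cited range. It does not show that the trial is too small for the much larger effect reported in the cited comparison.

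**What to change.** Keep 500 patients and replace the power sentence in the Statistical Analysis section with one that names the conventional-arm rate. For example:

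> With 250 patients per arm and a two-sided α of 0.05, the trial has 80% power to detect a difference of about 12.5 percentage points if first-attempt success with the conventional catheter is 46%, and 10.6 points if it is 71%. Power for a 10-point difference is 61% to 75% across this range.

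If 75% was the assumption, state it, give its basis and explain why it exceeds the 46% to 71% in the Background. Name the test as well, so that the calculation can be repeated.

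The cost is a sentence or two and a less favourable stated figure. No patients, procedures or analyses change. The rewording makes the claim accurate but does not restore 80% power for 10 points; if the sponsor wants that, the per-arm sizes in the table above apply.
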